9.3.1 Episodes of CPA/EE and hormonal contraceptive use

The duration of each CPA/EE and hormonal contraceptive prescription will include the medication-free days, if applicable. For CPA/EE, which is dosed in cycles of 21 days on medication and a 7-day interval without medication, the duration of one blister pack will thus be 28 days and the duration of a prescription will be the duration of one blister pack * the number of blister packs prescribed (see Figure 9.1). Most (if not all) oral hormonal contraceptives, patches and rings are also dosed in 28-day cycles with variations in the number of medication-free days. For intra-uterine devices, injections and implants the duration will be defined as the duration of effectiveness or until removal of the intra-uterine devices or implant when this is identified in the database. For each hormonal contraceptive the duration of effectiveness will be defined from the label.

Subsequent prescriptions of the same drug will be concatenated if the new prescription date precedes the end date of the previous prescription. The adjusted start date of the new prescription will be the day after the end date of the previous prescription. Subsequently, prescriptions of CPA/EE and hormonal contraceptives between index date – 365 days and end of follow-up will be converted into treatment episodes of uninterrupted use. In case of an interruption between two prescriptions, use of the drug will be considered interrupted and the treatment episode ends, i.e. no gap is allowed between two prescriptions.

Patients may have several treatment episodes of CPA/EE and hormonal contraceptives after treatment onset.

[figure not shown]

Figure 9.1 Cycles, prescriptions and treatment episodes of CPA/EE and hormonal contraceptives

Each box indicates one cycle, e.g. a blister pack. Subsequent cycles constitute a prescription, and subsequent prescriptions constitute a treatment episode.

9.3.2 Definition of switching and (potential) concomitant use of CPA/EE and hormonal contraceptives

Switching between hormonal contraceptives will be defined as a prescription date of a new hormonal contraceptive preceding the end date of a previous episode of another hormonal contraceptive. As most hormonal contraceptives are given in cycles, the assumption will be that the user will finish a cycle (e.g. the blister pack or patch) of the first hormonal contraceptive before starting a new one. Hence, the adjusted end date of the previous episode will be the end date of the cycle during which the new prescription was observed. The adjusted start date of the new hormonal contraceptive will be the day after the adjusted end date of the previous.

If the previous contraceptive is not given in cycles (e.g. progestogen-only pills, intra-uterine devices, implants) the adjusted end date will be the day before the date of the new prescription and the start date of the new hormonal contraceptive will not be adjusted.

For all episodes of CPA/EE, overlap with hormonal contraceptive episodes will be assessed similarly to the switches between hormonal contraceptives. However, as concomitant use of CPA/EE and hormonal contraceptives is among the study objectives, we will not define a switch but classify in terms of (potential) concomitant use. The days between the adjusted end date and the original end date of a truncated episode will be classified as:

- Potential concomitant use: (see Figure 9.2) when a “switch” from CPA/EE to a hormonal contraceptive *or vice versa* occurs during the last prescription within a treatment episode
- Concomitant use: when both start and end date of a hormonal contraceptive episode lie between start and end date of a CPA/EE episode *or vice versa*; or when a “switch” from CPA/EE to a hormonal contraceptive *or vice versa* precedes the last prescription within a treatment episode.
- Non-concomitant use: both start and end date of a hormonal contraceptive episode lie outside a CPA/EE episode (i.e. before or after both start and end date of a CPA/EE episode).
- No use of hormonal contraceptives (no observed treatment episodes of hormonal contraceptives within 365 days before the index date until end of follow-up).

Because the validity of estimating duration differs between administration routes (oral, intra-uterine, implant, injection, ring and patch) concomitant use will be computed separately and presented separately in text or tables, depending on the numbers observed.

[figure not shown]

Figure 9.2 Definition of potential concomitant use of CPA/EE and hormonal contraceptives

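### Read literally, the contraceptive-to-contraceptive switch rule removes refills dated after the switch, so a CPA/EE course taken over them can be classed non-concomitant

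*Protocol*

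**What the plan says.** Section 9.3.1 builds episodes from prescriptions. It sets the pack length ("the duration of one blister pack will thus be 28 days") and the chaining rule: "Subsequent prescriptions of the same drug will be concatenated if the new prescription date precedes the end date of the previous prescription". The refill then starts the day after the earlier supply ends, and no gap is tolerated within an episode. The note to Figure 9.1 gives the hierarchy: "Subsequent cycles constitute a prescription, and subsequent prescriptions constitute a treatment episode".

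Section 9.3.2 defines a switch between contraceptives as "a prescription date of a new hormonal contraceptive preceding the end date of a previous episode of another hormonal contraceptive". For products taken in cycles, "the adjusted end date of the previous episode will be the end date of the cycle during which the new prescription was observed". For products not taken in cycles, "the adjusted end date will be the day before the date of the new prescription". Neither sentence makes an exception for prescriptions of the first product dated after the switch.

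For CPA/EE against a contraceptive, the section says that overlap is assessed in a similar way but is classified rather than called a switch: "The days between the adjusted end date and the original end date of a truncated episode will be classified as" potential concomitant, concomitant and so on. One route to concomitant use is a switch that "precedes the last prescription within a treatment episode".

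**The concern.** The reason given for truncation is that a woman finishes her current cycle before starting the new product. That justifies disregarding packs already in hand. It does not cover supply of the first product collected after the supposed switch, because a later refill is evidence against a switch. The CPA/EE rule in the same section accepts this: a refill after the second drug appears makes the use concomitant. So the same pattern of records is read in opposite ways, depending on whether the second drug is CPA/EE or another contraceptive.

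What is at stake is the classification of CPA/EE courses that begin later. If the first contraceptive has been cut back to an early cycle, a course started while it was still being refilled meets no contraceptive episode. Concomitant use is one of the main objectives in section 8.1 and the subject of the extension in section 8.2. In these cases the error can only lower the count.

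**Working it through.** The protocol gives no figure to reproduce. The check applies the rules of 9.3.1 and 9.3.2 to invented prescription dates. The 28-day pack is from the protocol; every date and pack count is an assumption.

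**Main example.** Contraceptive A, 3 packs (84 days) each time, is prescribed on days 0, 80 and 164. Each refill date precedes the end of the running supply, so the adjusted supply periods are:
- days 0–83
- days 84–167
- days 168–251

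This is one episode of 3 × 84 = 252 days. One pack of contraceptive B is prescribed on day 30. CPA/EE, 3 packs, is prescribed on day 110 and covers days 110–193.

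*As written:*
- Day 30 lies in A's second cycle (days 28–55), so A ends on day 55 and B runs days 56–83.
- Days of A removed: 251 − 55 = 196, which is 196/252 = 78%. They include the supply collected on days 80 and 164.
- CPA/EE on days 110–193 meets neither A (to day 55) nor B (to day 83). It is non-concomitant, with 0 overlap days.

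*With A's later refills kept:*
- A runs again on days 84–251, and CPA/EE lies wholly inside it. It also starts before A's last prescription (day 164). Either test makes it concomitant.
- Calendar overlap is 193 − 110 + 1 = 84 days. The protocol's own duration measure uses adjusted dates, so its day count would differ; the class would not.

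**Dependence on the supply of B** (same A, B prescribed on day 30):

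| B | CPA/EE days | As written | Overlap with A lost |
|---|---|---|---|
| 1 pack, days 56–83 | 110–193 | non-concomitant, 0 days | 84 days |
| 3 packs, days 56–139 | 110–193 | potential concomitant through B, 30 days | 84 days |
| 3 packs, days 56–139 | 150–233 | non-concomitant, 0 days | 84 days |
| 6 packs, days 56–223 | 150–233 | potential concomitant through B, 74 days | 84 days |

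**Range.** B was moved over days 1–79 and the CPA/EE start over days 84–251, giving 79 × 168 = 13,272 combinations. In every one, CPA/EE overlaps A's later supply. As written, the course is non-concomitant only in 95% of combinations with 1 pack of B, 67% with 3 packs and 17% with 6 packs. The combinations are unweighted. They show that the result does not hang on one choice of dates; they do not estimate how often it occurs.

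**The case against.** **Order of steps.** The protocol does not say that CPA/EE overlap is assessed after contraceptive episodes have been truncated against each other. It keeps the notion of an original end date. If CPA/EE were compared with the untruncated episode A, the main example would already be concomitant. Nor does the text say that records are deleted; it adjusts an end date. A programmer working in date order could treat the refill of A as a switch back and keep the supply. This stands as a limit: the consequence rests on an order that is implied. But nothing in 9.3.2 directs the more favourable reading, and Table 5.1 (no. 5) records that centres have already interpreted this section differently.

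**Women who really change product.** A reader might infer that anyone who tries a second contraceptive and returns to the first loses all later supply. The documents do not support that. In the example, a woman who took B on days 56–83 still has one pack of A, uses it on days 84–111 and needs a refill about day 112. Recorded supply of A ended on day 83, so there is a gap, and under 9.3.1 a new episode begins that the earlier cut does not touch. With refills on days 112 and 192 that episode runs days 112–279, and CPA/EE on days 150–233 is concomitant as written. The problem needs A to be refilled on schedule, without a gap, after B was prescribed.

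**THIN.** Table 5.1 (no. 5) says that THIN builds contraceptive episodes only after the index date, so a switch before index cannot act there. THIN supplied 2,341 of 1,401 + 2,341 + 261 = 4,003 new users in 2014 (58%), but 2,760 of 7,876 + 2,760 + 495 = 11,131 in 2011 (25%). PHARMO and HSD are exposed both before and after index.

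**Injections.** The same result might be inferred for women on regular injections who are prescribed a pill once. That depends on the labelled duration and on injections never being late. The protocol gives no duration, so the case cannot be worked out.

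**Comparability.** The extension was requested with the earlier methodology, and an unchanged rule treats all years alike. That argues for keeping the rule as a comparator. It does not make the classification right, and it does not guarantee the same error in each year.

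**Conclusion.** The point holds in a limited form. Read literally, 9.3.2 ends the whole previous contraceptive episode even when uninterrupted refills of that product follow, and this conflicts with how the same section reads such refills against CPA/EE. Provided that CPA/EE overlap is assessed on the truncated episodes, a CPA/EE course started over those refills is non-concomitant when the second contraceptive does not itself overlap it. Where the second contraceptive does overlap it, only the overlap with the first product is lost.

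Concomitant use is therefore under-counted, but only among women who keep refilling the first product without a gap and, in THIN, only for contraceptive use after index. The protocol gives no count of women with two contraceptives in the window. It would go too far to say that the study's concomitant-use figures are materially wrong, or that a primary safety endpoint is biased: this is a descriptive utilisation study, and concomitant use is one of five main objectives. The ambiguity should still be resolved before the extension is analysed, because the rule as it stands can put a woman in the wrong class.

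**What to change.** In 9.3.2, state that a previous contraceptive episode is truncated at a switch only if no prescription of that product is dated after the switch. Otherwise, end only the prescription running at the switch and start a new episode at the next prescription date of the first product. State that this is done before overlap with CPA/EE is assessed.

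Apply the rule to every study year from 2011 to 2017 (2013 is excluded by design) and report the rule as now written as a sensitivity analysis, so that the trend stays comparable with the earlier report.

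The cost is a short change of text, a program change at each centre and re-derivation of 2011, 2012 and 2014. No new data are needed, and the concomitant-use shells (Tables 15.4 to 15.6) are blank for every year. Some women will have more contraceptive episodes than under the present rule.

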- For the study extension: demographic characteristics as above, duration of CPA/EE use and concomitant use of hormonal contraceptives

Data sources: The study will be conducted in the following databases:

- PHARMO Database Network (PHARMO) – The Netherlands
- The Health Improvement Network (THIN) – United Kingdom
- Health Search Database (HSD) – Italy

Study size: In a preliminary analysis of 2011-2012 about 9000 new users of CPA/EE were observed in the three databases.

Data analysis: Patient, treatment and diagnosis characteristics will be reported descriptively. Categorical data will be presented as counts (n) and proportions (%). Continuous data will be presented as means with standard deviation (SD) and as medians with inter quartile range (IQR) when appropriate. Prescriptions of CPA/EE and hormonal contraceptives between index date – 365 days and end of follow-up will be converted into treatment episodes of uninterrupted use. In case of an interruption between two prescriptions, use of the agent will be considered interrupted and the treatment episode ends, i.e. no gap is allowed between two prescriptions. Patients may have several treatment episodes after treatment onset. Episodes of the two classes (CPA/EE and hormonal contraceptives) may overlap, indicating concomitant drug use when there is complete overlap. Partial overlap will be defined as ‘potential concomitant use’. Results will be presented for the 2011/2012 users together and stratified by year of diagnosis.

Milestones: The data of 2014 for the three databases (THIN, PHARMO, HSD) will become available mid-2015. Considering a time period of ca. 6 months for analysis of the data and report writing, a final study report is planned for March 2016. Regulatory submission of the study protocol for the database Drug Utilization Study is planned for the third quarter of 2014. An interim report containing 2011/2012 results from the first run will be delivered in Q3 2015.

The data of 2017 for the three databases (THIN, PHARMO, HSD) will become available mid-2018. The study report for the additional objectives will be ready in Q1 2019.

5. Amendments and updates

Table 5.1 Amendments and updates to the Study Protocol

| Number | Date | Section of Study Protocol | Amendment or update | Reason |
|--------|------|---------------------------|---------------------|--------|
|--------|------|---------------------------|---------------------|--------|

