| | PHARMO | THIN | HSD |
|--|---|---|---|
| | 2011/2012 starters N = n (%) | 2011/2012 starters N = n (%) | 2011/2012 starters N = n (%) |
| Type of CPA/EE | | | |
| Diane 35 | | | |
| Generic | | | |
| Unknown | | | |
| CPA/EE prescriber | | | |
| GP | | n (100%) | n (100%) |
| Dermatologist | | n.a. | n.a. |
| Gynaecologist | | n.a. | n.a. |
| Other specialist | | n.a. | n.a. |
| Unknown | | n.a. | n.a. |
| Number of CPA/EE episodes during follow-up | | | |
| 1-2 | | | |
| 3-4 | | | |
| ≥5 | | | |
| mean ± SD | | | |
| median (IQR) | | | |
| Summed duration of CPA/EE use (months)* | | | |
| <6 | | | |
| 6-12 | | | |
| 13-24 | | n.a. | n.a. |
| mean ± SD | | | |
| median (IQR) | | | |
| Concomitant use of CPA/EE and HC**† | | | |
| Concomitant | | | |
| Potential concomitant | | | |
| Non-concomitant | | | |
| No use of HC | | | |
| Duration of concomitant use of CPA/EE and HC**† | | | |
| ≤28 days concomitant use | | | |
| >28 - 84 days concomitant use | | | |
| >84 days concomitant use | | | |
| mean ± SD | | | |
| median (IQR) | | | |
| Duration of potential concomitant use of CPA/EE and HC**† | | | |
| ≤28 days potential concomitant use | | | |
| >28 - 84 days potential concomitant use | | | |
| >84 days potential concomitant use | | | |
| mean ± SD | | | |

| | |
|--------------|--|
| median (IQR) | |
|--------------|--|

| |
|--|
| |
|--|

*follow-up is maximum 24 months; †users of CPA/EE may occur in multiple categories of concomitant use if more than one episode of HC is observed.

Table 14.4 Treatment characteristics of new CPA/EE users in PHARMO, THIN and HSD in 2011, 2012 and 2014

| | PHARMO | | | THIN | | | HSD | | |
|--|-------------------------------|-------------------------------|-------------------------------|-------------------------------|-------------------------------|-------------------------------|-------------------------------|-------------------------------|-------------------------------|
| | 2011 starters N = n (%) | 2012 starters N = n (%) | 2014 starters N = n (%) | 2011 starters N = n (%) | 2012 starters N = n (%) | 2014 starters N = n (%) | 2011 starters N = n (%) | 2012 starters N = n (%) | 2014 starters N = n (%) |
| Type of CPA/EE | | | | | | | | | |
| Diane 35 | | | | | | | | | |
| Generic | | | | | | | | | |
| Unknown | | | | | | | | | |
| CPA/EE prescriber | | | | | | | | | |

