15.2 Concomitant use of hormonal contraceptives

15.2.1 Concomitant use of hormonal contraceptives in PHARMO

Table 15.4 Concomitant use of other HC among new CPA/EE users in PHARMO per calendar year

| | 2011 starters N=0,000 n (%) | 2012 starters N=0,000 n (%) | 2014 starters N=0,000 (%) | 2015 starters N=0,000 n (%) | 2016 starters N=0,000 n (%) | 2017 starters N=0,000 n (%) |
|---|--------------------------------------|--------------------------------------|------------------------------------|--------------------------------------|--------------------------------------|--------------------------------------|
| Number of CPA/EE episodes during follow-up 1 2 ≥3 mean ± SD median (IQR) Summed duration of CPA/EE use (months) ¹⁾ 0-3 4-6 7-12 mean ± SD median (IQR) | | | | | | |
| Concomitant use Concomitant and potential concomitant use ²⁾ Potential concomitant use Non-concomitant use No use of other HC Duration of concomitant use of other HC ≤28 days >28 - 84 days >84 days mean ± SD median (IQR) Duration of potential concomitant use of other HC (days) ≤28 days >28 - 84 days >84 days mean ± SD median (IQR) | | | | | | |

1) by definition, the follow-up and thus summed duration of use will not be longer than 12 months (see section 9.2).

2) A user may be concomitant and potential concomitant user at different times during CPA/EE use.

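### Section 9.3.2 sets no precedence between concomitant and potential concomitant use for nested episodes, and the abstract contradicts it on partial overlap

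*Protocol*

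**What the plan says.** Section 9.3.2 handles CPA/EE and hormonal contraceptive (HC) episodes as it handles switches between contraceptives. A new prescription issued before the running episode ends truncates that episode, and the days cut off are then classified. Three bullets matter here:

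- **Potential concomitant:** the switch, in either direction, "occurs during the last prescription within a treatment episode".
- **Concomitant:** "both start and end date of a hormonal contraceptive episode lie between start and end date of a CPA/EE episode", or vice versa. A second limb adds a switch that comes before the last prescription of the episode.
- **Non-concomitant:** "both start and end date of a hormonal contraceptive episode lie outside a CPA/EE episode", with a bracket explaining this as before or after both CPA/EE dates.

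The section gives no order of precedence. It also does not say whether original or adjusted dates decide that one episode lies inside another.

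The abstract, under Data analysis, uses a different criterion: "Episodes of the two classes (CPA/EE and hormonal contraceptives) may overlap, indicating concomitant drug use when there is complete overlap". The next sentence, beginning "Partial overlap will be defined as", assigns all partial overlap to potential concomitant use.

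Section 9.3 also reports the duration of concomitant and of potential use, each in classes of up to 28, over 28 to 84, and over 84 days.

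**The concern.** Section 8.2 makes the 2011-2017 trend in concomitant use an objective of the extension, and Table 5.1 (entry 6) records that the regulator asked for patterns of concomitant use to be compared over time. The split between concomitant and potential use carries that comparison.

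If one pair of episodes satisfies two bullets, or the abstract and the body give different answers, the reported split depends on which sentence a programmer follows. Three centres work on three databases with local programs, and the earlier years were run before the extension. A difference between databases, or a change between runs, could then reflect coding rather than prescribing.

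**Working it through.** The protocol has no figure to reproduce here, so the check applies the stated rules to worked episodes. The 28-day pack comes from section 9.3.1. The numbers of packs and the prescribing days are assumptions chosen for illustration. Days are counted from 0 unless stated.

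**Case A: nested in the only prescription.** One CPA/EE prescription of 6 packs lasts 6 × 28 = 168 days, days 0-167. A 3-pack HC (3 × 28 = 84 days) is prescribed on day 30.

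- Day 30 falls in the cycle of days 28-55. The adjusted CPA/EE end is therefore day 55, and the adjusted HC start is day 56.
- HC runs on days 56-139 (adjusted) or 30-113 (original). Both lie inside 0-167, so the nesting limb gives *concomitant*.
- The switch falls in the only, hence the last, CPA/EE prescription, so the other bullet gives *potential*.
- The days classified run from the adjusted to the original CPA/EE end: 167 − 55 = 112 days. Only 84 days of HC were supplied. The duration class becomes over 84 days instead of over 28 to 84.
- The date basis matters. Against the original CPA/EE end (day 167) the HC episode is nested. Against the adjusted end (day 55) an HC start on day 56 leaves no overlap at all, and the nesting limb could never apply.

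**Case A in reverse: long-acting HC recorded once.** Suppose a device, assumed to be effective for 5 years, is in place before an 84-day CPA/EE episode and outlasts it. The CPA/EE episode is nested in the HC episode, so the vice versa wording gives *concomitant*. CPA/EE also starts during the device's only prescription, so the first bullet gives *potential*.

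**Case B: partial overlap before the last prescription.** Three consecutive 3-pack CPA/EE prescriptions cover days 0-83, 84-167 and 168-251. HC is prescribed on day 60 and continues past day 251.

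- Day 60 falls in the cycle of days 56-83, so the adjusted HC start is day 84.
- Overlap is days 84-251, which is 251 − 83 = 168 days.
- The last CPA/EE prescription starts on day 168, so the switch precedes it and 9.3.2 gives *concomitant*.
- The HC episode outlasts CPA/EE, so the overlap is partial and the abstract gives *potential*.

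**How often the rules collide on an assumed grid.** The grid takes 1-4 CPA/EE prescriptions of 28, 84 or 168 days, 1-4 HC prescriptions of 28 or 84 days, and every start day that produces an overlap, on unadjusted dates.

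| CPA/EE prescription length | Overlapping pairs | Two categories within 9.3.2 | 9.3.2 concomitant, abstract potential |
|---|---|---|---|
| 28 days | 6,688 | 359 (5.4%) | 1,479 (22.1%) |
| 84 days | 11,168 | 359 (3.2%) | 3,047 (27.3%) |
| 168 days | 17,888 | 1,930 (10.8%) | 3,162 (17.7%) |

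These are shares of an artificial grid in which every start day counts equally. They show that the conflicts are not confined to a single odd case, but they do not estimate proportions of women.

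**The case against.** Several points on the other side stand.

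- **Opposite categories.** A reader might infer that an HC episode spanning the whole CPA/EE episode is both concomitant and non-concomitant, since both its dates lie outside. The text does not support this. The bracket ordinarily means wholly before or wholly after, and vice versa places a spanning episode under concomitant. The firm conflict is between two adjacent grades of overlap.
- **Table layout.** A reader might see a contradiction between the Table 14.3 footnote, "users of CPA/EE may occur in multiple categories of concomitant use if more than one episode of HC is observed", and the row in Tables 15.4-15.6 headed "Concomitant and potential concomitant use". The two are compatible ways of showing women with several episodes, and the Annex 2 shells use one layout for all years.
- **Single-prescription episodes.** It is tempting to say that every overlap in such an episode is affected. It is not. If HC starts during the only CPA/EE prescription and outlasts it, 9.3.2 and the abstract both give potential. Full nesting is needed.
- **Table 5.1, entry 5.** It shows that section 9.3.2 has been interpreted differently between centres, but on whether HC episodes were built before the index date. It does not show centres choosing different bullets for the same overlap.

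It can also be argued that the abstract resolves case A, because "indicating concomitant drug use when there is complete overlap" points nested episodes to concomitant, and that Figure 9.2, not available here, may illustrate potential use. The first argument is a good reason for choosing that precedence, but 9.3.2 does not state it. The same abstract sentences are also what contradict 9.3.2 in case B, which a figure in 9.3.2 cannot cure.

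**Conclusion.** Two defects hold on the text. Within 9.3.2, an episode nested in the other drug's last or only prescription meets both the concomitant and the potential definition, with no precedence. Between the abstract and 9.3.2, a non-nested overlap that begins before the last prescription is potential in one and concomitant in the other. A related consequence is that the truncation rule can count more days than the two supplies overlap (112 against 84 in case A).

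The effect is bounded. Both conflicts move women between two reported categories and leave the any-overlap total unchanged. The study is descriptive, so no test is affected. The protocol gives no data from which to estimate how many women would move. The worked cases rest on assumed pack counts and prescribing days; the conflicts themselves rest only on the wording.

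This is still more than missing detail. The stated rules give two answers for the outcome that carries the extension's trend, and it should be settled before that comparison is run.

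**What to change.** Keep the 9.3.2 categories, but make them ordered and exclusive:

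1. **Non-concomitant:** the HC episode lies wholly before or wholly after the CPA/EE episode.
2. **Concomitant:** one episode is nested in the other (this takes precedence), or the switch comes before the last prescription.
3. **Potential:** any remaining overlap, that is, a non-nested switch during the last prescription.

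Then:

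- State whether original or adjusted dates decide nesting.
- Cap the concomitant days of a nested episode at the days the two supplies overlap. Case A then counts 84 days.
- Rewrite the abstract to match 9.3.2.
- Have all three centres confirm that they use this rule, and apply it to 2011, 2012, 2014 and 2015-2017.
- Show episodes nested in the last or only prescription on a separate line, so that results remain comparable with the earlier report.

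Moving nested episodes to potential would also remove the ambiguity. However, it would redefine the outcome against the nesting limb of 9.3.2 and the abstract's complete-overlap rule, and it would sit badly with the regulator's request, recorded in Table 5.1, to keep the earlier methodology.

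The cost is protocol wording and re-running existing programs for the earlier years; no new data are needed. Some earlier percentages may shift between the two categories and would need a footnote.
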